Participants will not be removed for treatment failure, as part of our goal is to investigate whether the TES program is easy to use by, and interesting to patients as part of the acceptability survey and review of module completion. Participants will be removed from the study if they no longer meet the inclusion criteria. For example, if a patient's status changes to involuntary they will be removed from further participation, but any data gathered up until that point will be used in analysis.

- g. Description of what happens to participants receiving therapy when study ends or if a participant's participation in the study ends prematurely.

Participants in the TES group will no longer have access to the computer-based program after the study ends, or if their participation ends prematurely, but all patients will receive standard inpatient care and referral to post-discharge treatment.

5. Inclusion/Exclusion Criteria

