Potential participants will be patients voluntarily admitted to the JHH Motivated Behaviors Unit (MBU), whose patients primarily present from the East Baltimore community. Eligibility criteria include self-report of drug or alcohol use in the 30 days prior to admission, diagnosis of both a substance use disorder and other psychiatric illness, a proficiency in English, and an ability to provide informed consent. Patients who are actively psychotic, or cognitively impaired with a Mini-Mental State Examination (MMSE) score of 25 or less will be excluded. After listening to a recording of the content of the informed consent form, participants must be able to obtain a score of 100% on a consent quiz after up to 3 attempts, with a chance for remediation between attempts. We will consent 150 participants with a plan to accrue about 130 persons in order to allow for drop outs or other early removals from the study and have a total of at least 100 participants. Our screening process will involve a study team member using the electronic medical record to ensure that the patient does indeed meet criteria for inclusion. The potential participant must be willing to participate and agree to the procedures in the consent form, such as allowing the team to contact his/her post-discharge provider(s). The person should also be willing to complete the risk assessment module through the TES program and at least one other TES module if randomized to that treatment arm, and to seek post-discharge treatment. Patients must have an email address, and if they do not have one they will be assisted in setting up an email account for distribution of surveys post-discharge. If a person does not set up an email account, surveys can be administered by phone post-discharge. The preferred method of payment for participant incentives will be Bank of America prepaid debit cards, so that

funds can be electronically deposited after they are discharged from the hospital. Participants will be required to sign an agreement regarding use of these cards. If necessary in certain cases, participants may receive other physical or electronic gift cards.

6. Drugs/ Substances/ Devices

- a. The rationale for choosing the drug and dose or for choosing the device to be used.

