TES acceptability will be rated on a scale of 0-10, and will be analyzed by mean and SEM. Comparison of hospital ratings will be performed using a paired t-test. The hypothesis is that the TES group will have significantly higher ratings than the TAU group. Based on a previous study of acceptability of TES compared to standard treatment⁷, a power analysis with alpha = 0.05

indicates that 50 persons per group is adequate to demonstrate an effect size of 0.313, where estimated power is 0.87.

d. Early stopping rules.

Those patients who leave against medical advice without a follow up appointment will be excluded from further participation in the study and thus can be included in analysis of any surveys completed during their stay, but not the post-discharge surveys. Any participants who no longer meet inclusion/exclusion criteria (e.g. MMSE score falls to 25 or below) will be removed from the study.

8. Risks

a. Medical risks, listing all procedures, their major and minor risks and expected frequency.

N/A

b. Steps taken to minimize the risks.

N/A

c. Plan for reporting unanticipated problems or study deviations.

These will be reported promptly to the IRB if any arise, though this is unexpected.

d. Legal risks such as the risks that would be associated with breach of confidentiality.

Given the content of the questionnaires there is little anticipated legal risk.

e. Financial risks to the participants.

N/A

9. Benefits

a. Description of the probable benefits for the participant and for society.

The participants in the TES group will benefit from participating in this study through increasing the skill set needed to work in recovery. Patients such as those participating in this study who have a substance use disorder as well as another psychiatric illness will benefit from the findings of this study as it will help us to better understand the needs of this population and whether this treatment will help them to be more engaged in their recovery. Similarly, this research will help the field and society through advancing what is currently known about psychiatric services for treating dually diagnosed patients, and thus working to reduce the mental and physical health complications, financial burden and disability caused by addiction in the community.

10. Payment and Remuneration

a. Detail compensation for participants including possible total compensation, proposed bonus, and any proposed reductions or penalties for not completing the protocol.

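### Randomised participants are removed after enrolment with no stated place in the 30-day enrolment analysis, and sections 4.f, 5 and 7.d leave open which eligibility criteria can trigger removal

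*Combined protocol and SAP*

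**What the plan says.** Removal is stated twice. Section 4.f: "Participants will be removed from the study if they no longer meet the inclusion criteria". Its example is a patient whose status becomes involuntary; for that patient, "they will be removed from further participation, but any data gathered up until that point will be used in analysis". Section 7.d: "Any participants who no longer meet inclusion/exclusion criteria (e.g. MMSE score falls to 25 or below) will be removed from the study". Section 7.d also ends participation for patients who leave against medical advice without a follow-up appointment. Their in-hospital surveys may be analysed, but not the post-discharge ones.

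Section 5 lists the eligibility criteria. Besides voluntary admission and the MMSE limit, one criterion is that the person is "willing to complete the risk assessment module through the TES program and at least one other TES module if randomized to that treatment arm". Another, for both arms, is willingness to look for outpatient care after leaving hospital.

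Section 4.f also limits removal. The sentence just before the rule begins "Participants will not be removed for treatment failure, as part of our goal is to investigate whether the TES program is easy to use by"; it then turns to patients' interest in the program.

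Section 7.a makes TES acceptability, measured by self-report and by usage, the primary outcome. Section 7.b makes outpatient enrolment at 30 days after discharge a secondary outcome. No section defines an analysis set or says how a removed participant counts in the 30-day outcome.

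**The concern.** Removal under 4.f and 7.d can happen after randomisation. The two explicit triggers (involuntary status, MMSE of 25 or below) and the against-medical-advice rule all take people out before the 30-day outcome is due. Patients who leave against advice with no appointment seem unlikely to enrol in outpatient care, so that exclusion is probably related to the outcome. If their enrolment is never looked up, the 30-day rates describe a selected subset of each arm.

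The second problem is scope. Neither statement of the rule says which criteria are re-applied; each gives only an example. Taken literally, the rule covers the willingness criteria. Willingness to do TES modules is closely tied to the primary outcome and can lapse only in the TES arm. Willingness to seek care is closely tied to 30-day enrolment. The trial is unblinded (4.c), so whoever judges that a criterion has lapsed may know the arm. At stake is whether a difference in 30-day enrolment can be attributed to TES.

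**Working it through.** **The plan's own allowance.** Section 5 plans to accrue about 130 to end with at least 100, allowing for drop-outs and early removals. That is 130 − 100 = 30 people, or 1 − 100/130 = 23.1%. It covers losses of every kind and is not a removal rate under this rule. The power statement in 7.c does not depend on the rule and is not used here.

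**What removal loses.**

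| Data | Status after removal |
|---|---|
| Usage and ratings already recorded | Kept (stated in 4.f for the involuntary-status example) |
| Pre-discharge rating, if removed mid-stay | Not collected |
| Later TES usage | Cut off, because 4.g ends access when participation ends early |
| Post-discharge surveys | Not collected; stated in 7.d for against-advice leavers |
| 30-day enrolment | Not addressed anywhere |

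**Illustrations.** The documents give no enrolment, removal or refuser figures, so every input below is assumed.

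*A. Removal in the TES arm only, no true effect.* Let p be the enrolment rate in both arms, r the fraction of the TES arm removed, and q the enrolment rate among those removed. The retained TES rate is (p − r·q)/(1 − r).

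- p = 0.50, r = 0.10, q = 0.30: (0.50 − 0.03)/0.90 = 0.522, a false gain of 2.2 points.
- p = 0.50, r = 0.20, q = 0.20: (0.50 − 0.04)/0.80 = 0.575, a false gain of 7.5 points.
- p = 0.50, r = 0.10, q = 0: 0.50/0.90 = 0.556, a false gain of 5.6 points. With 65 randomised per arm (130/2), two-sided type I error is 0.095 by normal approximation.

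Over p = 0.40 to 0.60, r = 0.05 to 0.20 and q = 0 to 0.20, the false gain runs from 1 to 15 points and type I error from about 0.05 to 0.42. With the removed kept in the denominator, the third case returns 0.90 × 0.556 + 0.10 × 0 = 0.50, and the bias is zero.

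*B. Masking.* Suppose 30% of TAU and 15% of TES become unwilling to seek care, none of them enrols, and 70% of the willing enrol. The true rates are 0.70 × 0.85 = 59.5% for TES and 0.70 × 0.70 = 49.0% for TAU, a difference of 10.5 points. Removing all the unwilling gives 70% against 70%.

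*C. Same removal in both arms.* If a fraction s of non-enrollers is removed in each arm, the observed rate is p/(p + (1 − p)(1 − s)).

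- True 40% and 60%, s = 0.5: 0.40/0.70 = 57% and 0.60/0.80 = 75%. The 20-point difference becomes 17.9.
- True 50% in both arms, s = 0.5: 0.50/0.75 = 66.7% in both, so no false difference.

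Equal removal therefore inflates the rates and distorts a real difference, but does not by itself create one.

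*D. Ratings.* If people removed before giving a rating would have scored 3 and the rest score 8, the full TES mean is 8 × 0.9 + 3 × 0.1 = 7.5 with 10% removed, or 8 × 0.8 + 3 × 0.2 = 7.0 with 20%. The observed mean is 8.0 in both cases.

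**The case against.** A reader might infer that the plan removes people on the outcome itself: that a TES patient who turns against the program, or any patient who decides against outpatient care, is taken out. The documents do not establish this. The willingness wording describes a potential participant at entry, and no procedure re-assesses it. Both removal examples apply to either arm. The treatment-failure sentence in 4.f can be read as a limit on the rule. Section 4.b declines to fix a number of modules, so low usage is not a stated ground for removal. The separate against-advice rule would be largely redundant if unwillingness to seek care already led to removal. Willingness is also not the same thing as usage or enrolment.

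Most of that stands, and removal for lost willingness remains only a literal reading. It is not excluded, however. Voluntary admission is also worded as an entry condition, yet 4.f uses its loss as the example of later removal. Section 7.d repeats the rule without the treatment-failure limit.

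A reader might also infer that TES usage and ratings are inflated because refusers disappear. For anything recorded before removal, the retention clause in 4.f points the other way; only later data are exposed. Finally, the illustrations follow from their inputs. The masking example in particular assumes that every unwilling patient is identified and removed.

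**Conclusion.** The point holds in limited form. The explicit removals and the against-advice exclusion leave randomised participants with no stated place in the 30-day comparison, so that comparison is not of the groups as randomised. This does not depend on how the willingness criteria are read. Whether those criteria can also trigger removal is unclear, and sections 4.f, 5 and 7.d must be reconciled.

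The size of the bias is unknown. The 2 to 8 point false gain (1 to 15 over the wider grid) needs removal confined to the TES arm, which the explicit triggers do not imply; the masking example needs complete removal of the unwilling. For a pilot this is a cheap and worthwhile correction, not a fault that must be repaired before the trial can be relied on.

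**What to change.** 1. State that the willingness criteria in section 5 apply at entry only and are not grounds for later removal, and reconcile 4.f and 7.d with the treatment-failure sentence.
2. State that participants removed from study activities stay in the analysis in their randomised arm.
3. Count each TES participant with the usage recorded, zero if none.
4. Ascertain 30-day enrolment for all randomised participants, including those who leave against medical advice, through the medical record and the program contact already planned in 4.a. Make an exception where consent is withdrawn or does not cover it, or the IRB bars it. Count those found not to have enrolled as not enrolled.

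Whether consent extends to follow-up after a change to involuntary status or a fall in MMSE cannot be judged from the documents and should be checked. None of this alters who stops study sessions for those reasons.

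The cost is a few sentences and a few more record look-ups. The downside is that TES ratings, usage and enrolment rates may look less favourable.

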Date: 4/14/16

Principal Investigator: [name]

Application Number: IRB0007923

NCT: 02674477

Title: Treatment Engagement With Technology-assisted Treatment

1. Abstract

Technology-assisted treatment, or TAT (e.g., online modules, mobile applications), shows promise for innovative assessment, prevention, and treatment of substance use disorders (SUDs). The widespread access to TAT makes it a potentially cost-effective and innovative option available for delivery in multiple settings. To date, there have been no published studies that investigate whether TAT is effective in patients with SUDs in addition to another psychiatric illness (dual diagnosis patients). Thus, we plan to pilot a computerized cognitive behavioral therapy (CBT) program called the Therapeutic Education System (TES) in dually diagnosed inpatients and allow them access to the program as outpatients as well. Our hypothesis is that those assigned to TES will have better program retention and outpatient attendance than those assigned to treatment as usual (TAU), because the patients using TES may be more engaged in the process of problem recognition and problem solving with regard to their mental health and substance use problems. This research will be valuable to better understand the treatment needs of this dually diagnosed population, including ways to keep them engaged in care.

2. Objectives

We propose to conduct a controlled study assessing: 1) whether exposure to TES during hospitalization is acceptable to dually-diagnosed patients, and 2) whether TES use affects post-discharge treatment retention.

3. Background

Several computerized contingency management and cognitive-behavioral interventions for SUDs have shown efficacy in single-site clinical trials, and TES has been shown to have efficacy in a clinical trial involving multiple community-based addiction treatment programs¹⁻⁴. We surveyed inpatients on two hospital-based dual diagnosis units at the Johns Hopkins Hospital (JHH) to assess their interest in, access to, and experience with TAT, as well as preferences for content and implementation. Preliminary data suggest that despite most patients having no previous TAT exposure, they would welcome TAT during and after hospitalization, and would consider it helpful. Some patients preferred face-to-face therapy alone, suggesting that TAT should not completely replace these services.

4. Study Procedures

a. Study design, including the sequence and timing of study procedures

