the primary drug of use is an opioid. Patients in the TES group will be taught how to use the web-based therapy while inpatient and provided access to the system while residing on Meyer 3 using a participant-specific username and password. Each person's account will be logged out at the end of their session on Meyer 3, and the laptops will not be used by other (non-study) patients, ensuring confidentiality. Participants will be encouraged to continue using the TES program after discharge by accessing the website with their login information. A reminder will be sent to them regularly via email or text message regarding their access to the program. They will be advised to log out after every session and close their browser, but to be aware that if someone were to track the history of the Internet browser, the HealthSim website would appear. Patients will be given a list of places available to use a computer for free, such as patient resource centers at JHH and the University of Maryland Hospital, as well as public libraries. The study team will have separate, password-protected access to user data within the TES program, though any patient identifiers will be kept separate from the program. HealthSim keeps user data confidential, and uses data at the minimum required for maintenance and support of the program's use by each site. Per HealthSim, "any such use, however, shall be conducted in accordance with all applicable law and regulations, including privacy regulations."

The TES program consists of a series of 65 interactive modules on substance use-related topics (e.g., effective problem solving; HIV and AIDS; drug refusal skills training). We expect it will take less than thirty minutes to complete each module. Patients will be able to access the program during 1-hour long sessions, as often as possible. We anticipate TES usage will amount to at least 2 hours per week. The assessment of TAT acceptability, self-efficacy and health-related quality of life will be re-administered prior to inpatient discharge, and then during follow up (as described below).

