Many patients discharged from the MBU receive referral appointments to the Community Psychiatry Programs (CPPs) at JHH or Johns Hopkins Bayview Medical Center (JHBM) for psychiatric care, and many also go to the Broadway Center (the primary outpatient site operated by JHH for substance use treatment). When possible and appropriate, these will be the preferred referral sites for study participants, as is current practice. Patient involvement with outpatient care (i.e. enrollment) at either CPP can be tracked via the Electronic Medical Record. We will also track patient retention at other mental health and substance use treatment programs that patients may be referred to, by contacting the program directly with the patient's consent.

b. Study duration and number of study visits required of research participants.

At the time of study enrollment and prior to discharge from the hospital, patients in both groups will be administered a survey that assesses acceptability of their inpatient and outpatient treatment, self-efficacy and health-related quality of life, drug and/or alcohol relapse, and the experimental group will also be assessed for their acceptability of TES.

Since the length of inpatient stay and other factors may vary across patients, we will not attempt to dictate the number of TES modules that should be completed but will attempt to ensure that all TES participants have experience with the program before they leave and will track and record the amount of usage during the inpatient stay.

c. Blinding, including justification for blinding or not blinding the trial, if applicable.

Blinding is not possible as those getting the intervention will be using the computer program whereas those that are in the control group will not.

- d. Justification of why participants will not receive routine care or will have current therapy stopped.

All patients will receive treatment as usual, so no routine care will be stopped.

- e. Justification for inclusion of a placebo or non-treatment group.

The TAU group will not receive the TES intervention, though they will still receive the typical treatment on the unit. A comparison of the survey responses and post-discharge program adherence of the TES and TAU groups will provide information as to whether the TES intervention is helpful.

- f. Definition of treatment failure or participant removal criteria.

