As noted above, TES has shown efficacy in clinical trials among patients with SUDs in community-based addiction treatment programs. The two-group randomized design with TAU as the comparison condition was selected to provide a clinically relevant evaluation of TES when used as a supplement to TAU. Since acceptability and effects on post-discharge follow up care are of primary interest in this pilot trial rather than mental health or drug use outcomes, any imbalance in amount of therapy delivered should not be relevant.

- b. Justification and safety information if FDA approved drugs will be administered for non-FDA approved indications or if doses or routes of administration or participant populations are changed.

N/A

- c. Justification and safety information if non-FDA approved drugs without an IND will be administered.

The Therapeutic Education System (TES) is not a physical/mechanical device; but it is a software program that is accessed through the Internet on any PC or Mac computer using a specific username and password. Our research subjects will use it through a site-specific license, so that their information is separate from other TES users. TES does not pose any significant risk to subjects as it is not an implant, is not used for sustaining human life, does not present potential for serious risk to the health, safety or welfare of a subject and will not be used substantially in diagnosing, curing, or mitigating disease. It is a treatment, but it is not the primary treatment modality that will be employed with patients who enroll in this pilot study. As therapy, it will only be used adjunctively to treatment as usual in the form of education, in a supervised manner. Thus, TES does not meet the definition for a significant risk device, but is a nonsignificant risk device.

7. Study Statistics

- a. Primary outcome variable.

Acceptability of TES, via both self-report and actual usage, will constitute the primary outcome measure for the randomized design portion of the study.

- b. Secondary outcome variables.

The enrollment rate for outpatient mental health and substance abuse treatment at 30 days post-discharge, and patient satisfaction regarding the hospital stay among both groups will be investigated as secondary outcomes.

- c. Statistical plan including sample size justification and interim data analysis.

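### The primary outcome in 7a exists only in the TES arm, so the TES-over-TAU hypothesis and the power of 0.87 in 7c belong to a both-arm rating that the plan never identifies, and the paired t-test named there does not fit

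*Combined protocol and SAP*

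**What the plan says.** Section 7a of the combined protocol and SAP defines the primary: "Acceptability of TES, via both self-report and actual usage, will constitute the primary outcome measure for the randomized design portion of the study". This corresponds to Objective 1 in section 2, "whether exposure to TES during hospitalization is acceptable to dually-diagnosed patients".

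The two arms do not both supply this outcome. Section 4e states: "The TAU group will not receive the TES intervention". Section 4b describes a survey at enrolment and before discharge, in which "patients in both groups will be administered a survey that assesses acceptability of their inpatient and outpatient treatment", and adds that "the experimental group will also be assessed for their acceptability of TES".

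Section 7c has TES acceptability scored from 0 to 10 and summarised by mean and SEM. It then names a paired t-test for comparing hospital ratings, predicts significantly higher ratings under TES than under TAU, and gives a power of 0.87 for 50 persons per group at alpha 0.05 and an effect size of 0.313. The effect size is credited to an earlier study that set the acceptability of TES against standard treatment. Neither the effect-size metric nor the sidedness of the test is given.

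The Abstract's hypothesis is a different between-arm claim, that "those assigned to TES will have better program retention and outpatient attendance than those assigned to treatment as usual". Objective 2 asks "whether TES use affects post-discharge treatment retention". Section 7b lists enrolment in outpatient treatment at 30 days and satisfaction with the hospital stay as secondary outcomes, and 7c gives 30-day enrolment neither a test nor a power.

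**The concern.** The primary is tied to the randomised part of the study, yet randomisation gives it nothing to be compared with: a TAU patient has no TES rating and no TES usage. The between-arm hypothesis and the per-group power that follow in 7c must therefore concern something else, and the plan does not say what.

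Two things are at stake. A reader may credit the 0.87 to the primary, which has no between-arm contrast. And because several both-arm ratings could serve as the tested variable, the choice could be made after the data are seen. The named test adds to this: a paired t-test suits change within a person, not a comparison of two separate groups of people.

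**Working it through.** **Which outcome can carry the hypothesis?**

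| Measure | In TAU? | Status in section 7 | Timing in the documents |
|---|---|---|---|
| TES rating, 0 to 10 | No (4b, 4e) | Primary | TES arm only |
| TES usage | No (4e) | Primary | Inpatient stay, and access continues after discharge (4a) |
| Acceptability of inpatient and outpatient treatment | Yes (4b) | Not listed | Enrolment and before discharge |
| Satisfaction with the hospital stay | Yes (7b) | Secondary | No instrument or timing described |
| Acceptability of technology-assisted treatment in general | Yes, all volunteers (4a) | Not listed | Baseline, before discharge and follow-up |

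Only the last three rows can support a comparison of TES with TAU. The treatment-acceptability survey is closest in wording to the cited basis of the effect size. Satisfaction is the only one of the three that section 7 lists. General acceptability is measured repeatedly, so a paired test could fit its change within a person, but not its comparison between arms.

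**Reproducing the 0.87.** Inputs from 7c: 50 per group, alpha 0.05, effect size 0.313. For an independent two-sample t-test, the noncentrality is d × sqrt(n/2) = d × sqrt(25) = 5d, with 98 degrees of freedom.

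- 0.313 as Cohen's f: with two equal groups d = 2f = 0.626, noncentrality 3.13, power **0.873** two-sided (0.928 one-sided). This matches the plan.
- 0.313 as Cohen's d: noncentrality 1.565, power **0.341** two-sided (0.464 one-sided). Reaching 0.87 two-sided would need 196 per arm.
- Paired t-test at a standardised difference of 0.313, noncentrality 0.313 × sqrt(pairs): 0.583 with 50 pairs and 0.873 with 100 pairs. The second figure needs 100 pairs, not 50 persons per group.

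Setting power to 0.80 and 0.87 in the independent two-sided test with 50 per arm gives detectable d = 0.566 and 0.623.

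**Cost of the paired test.** If patients were paired arbitrarily across arms, the noncentrality would stay at 5d and the degrees of freedom would fall to 49. At d = 0.626, power goes from 0.873 to 0.866. The loss is small on average, but the p-value then depends on who is paired with whom, and the arms must be of equal size.

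**Precision of the primary as named.** With the TES arm alone (n = 50), the 95% CI half-width is t(0.975, 49)/sqrt(50) = 2.010/7.071 = 0.284 SD. The documents give no SD. If it is 2 to 3 points (an assumption), this is 0.57 to 0.85 points on the 0 to 10 scale.

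**30-day enrolment.** With 50 per arm, the half-width is 1.96 × sqrt[(p1(1−p1) + p2(1−p2))/50]. The documents give no rates, so these are assumptions:

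- equal rates: 18.0 points at 30% or 70%, 19.6 points at 50%;
- 30% versus 57%: 18.7 points; 70% versus 92%: 14.8 points.

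The range is about 15 to 20 percentage points. The two unequal pairs are differences detectable with 80% power. Over TAU rates of 30% to 70%, that detectable rise is about 22 to 28 points.

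**The case against.** This is a pilot, and a descriptive estimate in one arm answers Objective 1. That stands: the primary remains estimable, and its mean-and-SEM summary is workable. It does not rescue the comparative part, because the plan itself chose to state a directional between-arm hypothesis, a significance test and a power.

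A reader might infer that the sample size rests on a secondary outcome, since satisfaction with the hospital stay is the both-arm rating that section 7 lists. The documents do not support that as a conclusion. The effect size is credited to a study of acceptability, and the treatment-acceptability survey in 4b is at least as close to it. On that reading, the power belongs to a both-arm counterpart of the primary that section 7 omitted to name.

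A reader might also infer that 0.87 is a miscalculation and that the true power is 0.34. That does not follow either. The figure is reproduced under Cohen's f, and the documents do not contradict that metric. What is missing is the metric, so 0.34 is a conditional figure, not the likely power.

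Finally, the test, the effect-size metric and the unpowered enrolment outcome could be treated as separate matters. They belong here to the extent that each arises from 7c not linking test, power and outcome.

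**Conclusion.** The point holds and should be fixed. It is certain from the text that the 7a primary has no TAU comparator, that the TES-over-TAU hypothesis and the 50-per-group power cannot concern it, and that a paired t-test does not fit the comparison of two independent arms. Which both-arm rating was meant is not settled by the documents.

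The size depends on an unstated metric: power is 0.873 if 0.313 is Cohen's f and 0.34 if it is Cohen's d, two-sided with 50 analysed per arm. The one-arm primary is known to within 0.284 SD at n = 50. The enrolment figures rest on assumed rates.

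**What to change.** Change section 7 only:

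1. **7a.** Report the TES rating (mean with 95% CI) and TES usage as TES-arm estimates, with no between-arm test and no claim to the 0.87. Summarise usage separately for the inpatient stay and after discharge, because "Participants will be encouraged to continue using the TES program after discharge".
2. **7b and 7c.** Before outcome data are seen, name one pre-discharge rating collected in both arms, with its scale, as the outcome for the TES-over-TAU hypothesis and the power statement. The inpatient part of the 4b treatment-acceptability survey is the natural choice, because its collection in both arms before discharge is documented. Use satisfaction with the hospital stay only if it is confirmed to be collected in both arms before discharge on a numeric scale. The investigators decide whether this rating is a co-primary or a secondary outcome. Label the other both-arm ratings exploratory.
3. **Test.** Replace the paired t-test with an independent two-sample (Welch) t-test at two-sided 0.05, reporting the difference and its 95% CI.
4. **Power.** State metric and sidedness: 50 per arm detects d = 0.57 with 80% power and d = 0.62 with 87%. Say that 0.313 is Cohen's f or, if it is d, restate the power as 0.34.
5. **30-day enrolment.** Report the difference in proportions with its 95% CI, and say that the study was not sized for it.

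The cost is wording, plus a scoring rule fixed in advance if the chosen item does not give a single numeric score. The downsides are that TES acceptability becomes openly an uncontrolled estimate, and that the power statement may become less favourable.
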